11.1 Pharmacokinetic Analysis

11.1.1 Serum Concentration

Blood samples will be collected from each subject during this study for the determination of the PK of CT-P27 components (CT-P22 and CT-P23) administered as 45 mg/kg and 90 mg/kg. Blood samples for PK analysis will be drawn according to the following schedule.

Day of study period	Time point	Window
Day 1	Pre-infusion	Within 15 minutes prior to the beginning of the infusion
	End of infusion	+15 minutes
	1 hour after EOI	± 15 minutes
Day 2	24 hours after SOI	
Day 3	48 hours after SOI	± 4 hours
Day 8	168 hours after SOI	
Day 15	336 hours after SOI	± 2 days
Day 29	672 hours after SOI	
Day 57	1344 hours after SOI	± 5 days
Day 110 or EOS visit	2616 hours after SOI or EOS visit	

Abbreviations: EOI, end of infusion; SOI, start of infusion; EOS, end of study

Serum samples will be analyzed to determine the concentrations of CT-P27 components (CT-P22 and CT-P23) using a validated immunoassay.

Serum concentrations of CT-P27 components (CT-P22 and CT-P23) will be summarized for PK population by treatment group at each scheduled collection time using descriptive statistics; n, mean, SD, geometric mean, CV%, minimum, median, and maximum values. Mean serum concentration-time profiles of study drug will be plotted by treatment on linear and semi-logarithmic scales based on scheduled sample times. Individual concentrations, scheduled timepoints/actual sample collection times and deviations from scheduled collection times will be presented in data listing by treatment in PK population. Individual linear and semi-logarithmic concentration-time plots (based on scheduled sample times) with respective treatments will also be presented together. Since the placebo group has BLQ values for serum concentration, it will not be

Statistical Analysis Plan

summarized in tables and figures.

The BLQ values prior to the study drug administration will be treated as zero (0). For the BLQ values after study drug administration, the following rules will be applied;

- The BLQ values at the beginning of a subject profile (i.e. before the first incidence of a measurable concentration) will be assigned to zero (0).
- The BLQ values at the end of a subject profile (i.e. after the last incidence of a measurable concentration) will be set to missing.
- Single or 2 consecutive BLQs which fall between two measurable concentrations will be set to missing.
- Two or more consecutive BLQs in terminal phase will be set to zero.

11.1.2 Serum Pharmacokinetic Parameters

PK parameters for CT-P27 components (CT-P22 and CT-P23) will be summarized at each dose level (45 mg/kg and 90 mg/kg) using descriptive statistics. Summary statistics will include the number of observations (n), mean, SD, geometric mean, CV%, minimum, median, and maximum. Since the placebo group has BLQ values for serum concentration, it will not be summarized in tables. Dose proportionality for CT-P22 and CT-P23 will be assessed. PK parameters will be computed by non-compartmental methods using the appropriate validated [REDACTED]. PK parameters will be summarized in the Follow-Up CSR only.

The following PK parameters will be calculated using non-compartmental methods for CT-P22 and CT-P23:

- AUC_{0-last} ($h \cdot \mu g/mL$) calculated using the linear trapezoidal rule. This will be calculated over the study period.
- C_{max} ($\mu g/mL$) obtained directly from the observed concentration versus time data.
- $AUC_{0-\infty}$ ($h \cdot \mu g/mL$) calculated using the linear trapezoidal summation and extrapolated to infinity by addition of the last quantifiable concentration divided by the terminal rate constant: $AUC_{0-last} + C_{last}/\lambda_z$.
- t_{max} (h) obtained directly from the observed concentration versus time data.
- C_{last} ($\mu g/mL$) obtained from the last observed quantifiable concentration.
- λ_z (1/h) determined by linear regression of the terminal points of the log-linear concentration-time curve. Visual assessment will be used to identify the terminal linear phase of the concentration-time profile.
- $t_{1/2}$ (h) determined as $\ln 2/\lambda_z$.
- MRT (h), determined as $AUMC_{0-\infty}/AUC_{0-\infty}$, where $AUMC_{0-\infty}$ is the area under the first-moment curve evaluated from time zero to infinite time.
- CL (L/h) calculated as the administered dose divided by $AUC_{0-\infty}$.
- V_z (L) calculated as $Dose/(\lambda_z \cdot AUC_{0-\infty})$, where dose is the IV dose.

The following PK parameters will be calculated for diagnostic purposes and listed, but will not be summarized:

$t_{1/2}$, Interval (h)	The time interval of the log-linear regression to determine $t_{1/2}$.
$t_{1/2}$, N	Number of data points included in the log-linear regression analysis to determine λ_z . A minimum of 3 data points will be used for determination.
Rsq	Coefficient of determination for calculation of λ_z . λ_z and related parameters ($AUC_{0-\infty}$, CL, MRT, $t_{1/2}$, V_z) will be listed and not summarized if Rsq is less than 0.800.
%AUC _{ex}	Percentage of $AUC_{0-\infty}$ obtained by extrapolation, calculated as $[(C_{last}/\lambda_z)/AUC_{0-\infty} \times 100]$. If the extrapolated area (C_{last}/λ_z) is greater than 20% of

CONFIDENTIAL

Statistical Analysis Plan

λ_z

$AUC_{0-\infty}$, then $AUC_{0-\infty}$ and related parameters (CL, MRT, V_z) will be listed and not summarized.

If the interval used to determine λ_z is smaller than 1.5-fold the estimated $t_{1/2}$, λ_z and related parameters ($AUC_{0-\infty}$, CL, MRT, $t_{1/2}$, V_z) will be listed but not summarized.

Any anomalous concentration values observed at pre-dose will be identified in the study report and used for the computation of AUC. PK parameters will be computed if the anomalous value is not greater than 5% of the C_{max} . If the anomalous value is greater than 5% of C_{max} , only the concentration values will be listed and no PK parameters will be calculated or analyzed.

PK parameters will be presented in data listings and summarized in tables for PK population by treatment group. The decimal places for each PK parameter that will be presented in the listing are as follows:

PK parameter	The decimal places
$AUC_{0-\infty}$	1
AUC_{0-last}	1
C_{max}	1
C_{last}	1
t_{max}	2
V_z	2
λ_z	5
$t_{1/2}$	1
$t_{1/2}$, Interval	1
$t_{1/2}$, N	0
CL	4
MRT	2
Rsq	2
%AUC _{ex}	1

Dose proportionality for CT-P22 and CT-P23 will be assessed for C_{max} and AUC_{0-last} using the Power model. For each of the parameters assessed, a plot of the log-transformed parameter value against the log-transformed dose will be constructed including the fitted line from the linear regression and the line of unity slope. The 95% confidence interval (CI) and P-value for the slope will be presented.

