and 10 PM, approximately]) and body temperature of subject will be also taken by site personnel at site at screening, Day 1 (prior to infusion), Day 2, Day 3, Day 5 and Day 8. Nasopharyngeal swab samples will be used for viral shedding based on quantitative polymerase chain reaction (qPCR) and cell culture. Those samples will be taken at screening, Day 2 (24 hours [± 4 hours] after the start of the study drug infusion), Day 3 (48 hours [± 4 hours] after the start of the study drug infusion), Day 5 (96 hours [± 4 hours] after the start of the study drug infusion), and Day 8 (168 hours [± 4 hours] after the start of the study drug infusion). Laboratory confirmation of influenza A infection will be defined as a positive result by qPCR or cell culture.

Safety Assessment:

For safety evaluations, subjects will be followed up from the time the ICF is signed until Day 110 (approximately 5 half-lives) after the administration of study drug. Safety assessments will occur throughout the study.

Adverse events (AE) or concomitant medications that are verified by the investigator will be recorded on the eCRF. Up to Day 8, any AE or concomitant medication will also be recorded by subjects on their diaries and the investigators will refer to the records for information. If there is any AE or concomitant medication after Day 8, subjects will be instructed to contact the Principal Investigator or sub-Investigator at any time.

If symptoms have not relieved up to Day 3, chest x-ray will be performed to determine presence of secondary complications of influenza A infection.

Subjects with suspicious ADE will be required to assess virus titer using the nasopharyngeal swab sample, Flu-iiQ™ and body temperature up to Day 8 after the day of ADE occurrence. If symptoms have not resolved or have worsened up to Day 8 after the day of ADE occurrence, same procedures will repeat.

Exploratory Assessment:

Blood sampling for PK analysis will be collected from the subjects on:

- Day 1 at pre-infusion (within 15 minutes prior to the beginning of the infusion), the end of infusion (+15 minutes), 1 hour (± 15 minutes) after the end of the infusion,
- Day 2 (24 hours [± 4 hours] after the start of the study drug infusion),
- Day 3 (48 hours [± 4 hours] after the start of the study drug infusion),
- Day 8 (168 hours [± 4 hours] after the start of the study drug infusion)
- Day 15 (± 2 days),
- Days 29, 57 and 110 (± 5 days) or at EOS visit

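### The linear trapezoidal rule, applied across 28- and 53-day gaps in the elimination phase, overstates AUC and understates CL, Vz and MRT by about 5%

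*SAP*

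**What the plan says.** SAP Section 11.1.2 defines AUC0-last as "calculated using the linear trapezoidal rule. This will be calculated over the study period". AUC0-∞ is "calculated using the linear trapezoidal summation and extrapolated to infinity by addition of the last quantifiable concentration divided by the terminal rate constant". Protocol Section 8.5.3 gives the same two definitions. Neither document offers a logarithmic or linear-up/log-down option.

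The other exposure parameters inherit this integral. CL is "calculated as the administered dose divided by" AUC0-∞, and Vz is dose over λz times AUC0-∞. MRT is AUMC0-∞ over AUC0-∞, where AUMC0-∞ "is the area under the first-moment curve evaluated from time zero to infinite time"; no integration rule is given for AUMC. λz comes from a regression on the log-linear terminal points.

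The table in SAP Section 11.1.1 places the Day 29 sample "672 hours after SOI", the Day 57 sample at 1344 hours and the last one at "2616 hours after SOI or EOS visit". Protocol Section 4.1 follows subjects "until Day 110 (approximately 5 half-lives) after the administration of study drug".

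**The concern.** The plan treats the terminal decline in two incompatible ways. It assumes exponential decline when it fits λz and adds the tail as Clast/λz. It then joins the same late points with straight lines to get the area beneath them. The chord between two points on a falling exponential lies above the curve, so every late trapezoid is too large. The excess grows quickly with the length of the gap in half-lives, and the longest gap has no sample inside it.

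Protocol Section 2.2 and SAP Section 1.1 say that PK information will be used in selecting doses for later studies. A bias from the integration rule does not average out over subjects. It also ties the reported AUC and CL to this sampling schedule, so the values would not line up with those of a study sampled differently. Within this study, two subjects with identical kinetics can get different values because their late visits fell on different days or because one lacks a quantifiable Day 110 sample.

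**Working it through.** The documents give no accuracy figure for AUC, so there is none to reproduce. The check compares the planned rule with the exact integral.

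**Inputs from the documents**
- Nominal sampling times (SAP 11.1.1): pre-infusion, end of a 1.5-hour infusion, 1 hour later, then 24, 48, 168, 336, 672, 1344 and 2616 hours.
- Late gaps: 672 − 336 = 336 h (14 days); 1344 − 672 = 672 h (28 days); 2616 − 1344 = 1272 h (53 days).
- Half-life, inferred: 110/5 = 22 days. The last gap is 53/22 = 2.4 half-lives.
- λz from at least three points (SAP 11.1.2); Days 29, 57 and 110 are used here.

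**Assumptions:** noise-free profiles; mono-exponential decline in the base case; linear rule for AUMC as well as AUC.

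**Error of one interval.** For decline at rate λ over a gap d, put x = λd. The exact area is C₁(1 − e⁻ˣ)/λ and the trapezoid is C₁(1 + e⁻ˣ)d/2. Their ratio is (x/2)/tanh(x/2). The interval's true share of AUC0-∞ is e^(−λt₁) − e^(−λt₂), with t₁ and t₂ its start and end (ignoring the short infusion). With λ = ln 2/22 = 0.0315 per day:

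| Interval | Gap (days) | x | Trapezoid/exact | Share of AUC0-∞ | Added to AUC0-∞ |
|---|---|---|---|---|---|
| Day 15 to 29 | 14 | 0.44 | 1.016 | 22.9% | +0.37 points |
| Day 29 to 57 | 28 | 0.88 | 1.064 | 24.3% | +1.55 points |
| Day 57 to 110 | 53 | 1.67 | 1.222 | 13.9% | +3.09 points |

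Earlier intervals add about 0.1 point. The sum is 0.37 + 1.55 + 3.09 + 0.1 ≈ 5.1.

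**Parameters at a 22-day half-life**
- AUC0-∞: +5.1%.
- AUC0-last: the tail beyond Day 110 is 3.2% of AUC0-∞, so 5.1/0.968 ≈ +5.3%.
- CL and Vz: 1/1.051 − 1 = −4.9%.
- MRT: −5.2% with linear AUMC; −4.9% if AUMC were exact.

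**Sensitivity**

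| Scenario | AUC0-∞ | CL | MRT |
|---|---|---|---|
| Half-life 15 days, mono-exponential | +7.0% | −6.5% | −3.6% |
| Half-life 30 days, mono-exponential | +3.4% | −3.3% | −4.9% |
| Half-life 15 to 30 days, with or without an assumed distribution phase (45% of initial level, half-life 1.5 to 3 days) | +3.4% to +7.9% | −3.3% to −7.3% | −3.6% to −5.8% |
| 22 days, Day 29, 57 and 110 visits moved by ±5 days | +3.9% to +7.4% | −3.8% to −6.9% | −4.9% to −7.9% |
| 22 days, profile ends at Day 57 | +2.0% | −2.0% | −3.7% |

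**Linear-up/log-down on the same samples.** The error is 0.0% in the mono-exponential case. With the 45% distribution phase it is at most about +1% for AUC0-∞ and −0.7% for MRT. With a wider assumed distribution phase (40% to 70% of the initial level, half-life 1 to 4 days) and a 22-day terminal half-life, it reaches about +1.7% and −1.4%. The linear rule gives +5.6% to +7.0% for AUC0-∞ over those same profiles.

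**The case against.** The case against acting concerns weight rather than direction.

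- **PK is exploratory and mainly descriptive.** The only inferential PK analysis is the power-model slope for Cmax and AUC0-last. Cmax is read from the data. If both dose groups share the same sampling times and half-life, the AUC bias is a common factor and cancels in the slope. λz, t1/2, tmax and Clast are untouched. The extrapolated share barely moves (3.2% true, 3.1% under the linear rule) and stays far from the 20% limit. All of this stands.
- **The half-life is inferred from a rounded phrase** that justifies the length of follow-up, and one value is applied to two antibodies. This stands, and it is why ranges are given. The sign of the AUC bias does not depend on the value.
- **About 5% presumes a quantifiable Day 110 sample.** SAP 11.1.1 sets BLQ values at the end of a profile to missing, so some profiles may end at Day 57, with a bias near 2%. This stands. It also means the bias can differ between subjects for reasons unrelated to clearance.
- **Sampling error may be as large.** With 20 subjects per dose and an assumed between-subject CV of 20% to 40%, the standard error of a group mean is 20/√20 = 4.5% to 40/√20 = 8.9%. That limits the practical effect, but random error is no reason to keep an avoidable systematic one.
- **Neither document names AUC, CL, Vz or MRT as the quantities that decide a dose**, and no threshold is shown that a 5% shift would cross. That is correct; the documents say only that PK information will be used.

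**Conclusion.** The concern holds. Under the planned rule and schedule, AUC0-last and AUC0-∞ are overstated, and CL, Vz and MRT understated, by about 5% each at a 22-day half-life. This rests on that inferred half-life, mono-exponential decline, nominal visit times and a quantifiable Day 110 value. Over the assumed 15-to-30-day range, with or without the 45% distribution phase, the AUC0-∞ bias is +3.4% to +7.9%; it falls to about +2% when a 22-day profile stops at Day 57. The absolute exposure values and their comparison with other studies are affected. The primary efficacy analysis is not, and the dose-proportionality slope is not when the two dose groups share sampling times and half-life. The change should be made, but it is not critical.

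**What to change.** In SAP Section 11.1.2, replace the linear trapezoidal rule with linear-up/log-down for AUC0-last and AUC0-∞: linear while concentrations rise, logarithmic while they fall. State the same rule for AUMC, which has none at present. Record the change in SAP Section 13, where the revised BLQ handling and the tighter extrapolation limit are already logged as departures from Protocol Section 8.5.3. PK parameters are summarised only in the Follow-Up CSR, so the amendment should be made before they are computed.

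The cost is one setting in the non-compartmental software and one SAP line, with no extra samples. The drawback is that results would not be directly comparable with any earlier CT-P27 study analysed by the linear rule. Listing the linear-rule values alongside deals with that.

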11.2 Immunogenicity Analysis

Immunogenicity will be assessed in the safety population by baseline and post-treatment serum measures of anti-CT-P27 component antibodies, CT-P22 and CT-P23 antibodies, using immunoassay. Immunogenicity assessments consist of both Anti-Drug Antibody (ADA) and Neutralizing Antibody (NAb) assays. The ADA

Statistical Analysis Plan

assay will follow a three-tiered approach consisting of (i) screening assay, (ii) specificity/confirmatory assay, and (iii) titration. The test outcome for the screening assay will be: {"Potential Positive" or "Negative"}. Samples that are "Potential Positive" in the screening assay will be undergone further testing in the specificity/confirmatory assay to determine if subjects are a true positive. The test outcome for the specificity/confirmatory assay will be: {"Reactive", "Negative", and "Not applicable (N/A)"}. "Reactive" indicates a true positive test outcome, "Negative" is considered negative and "N/A" indicates the assay was negative at the screening phase of the process. Subjects with a "Negative" test outcome for either screening or specificity/confirmatory assays will be considered negative for the overall ADA assessment. For further characterization, quantitative antibody level will be assessed by titration in confirmed positive samples. The ADA value of the CT-P22 and CT-P23 tagged assay will be transformed using a log transformation. Transformed ADA value can be obtained using $[\log_2(X/20)] + 1$ transformation.

Samples that are positive in the assessment will be analyzed further to conduct a NAb assessment. The same three-tiered approach of ADA assay will be applied to NAb assay. Transformed NAb value can be obtained using $[\log_2(X/10)] + 1$ transformation. If ADA or NAb titer values in the data are in inequality forms, the sign of inequality will be removed and then the values will be transformed.

Immunogenicity result for CT-P22 and CT-P23 are listed and summarized separately. The number and percentage of subject will be presented by treatment group and test at each scheduled time point for the safety population.

11.3 Other Exploratory Analysis

Blood sampling for assessment of anti-influenza antibodies (Hemagglutination inhibition) will be collected on Day 1 (at pre-infusion) and Day 29 (\pm 5days) or EOS visit (if a subject is early terminated from the study) in Subgroup (PK) Cohort.

Genotypic analysis on Hemagglutinin (HA) and Neuraminidase (NA) genes, and phenotype characterization of potential escape variants with regard to CT-P27 will be assessed using the nasopharyngeal swab samples.

11.3.1 HI Antibody

Individual HI antibody will be assessed repeatedly in each collection time (Baseline, Day 29) and the geometric mean value of those duplicated HI antibody results will be used in the analyses. The Geometric Mean Titer (GMT) and sample collection times will be presented in data listing by treatment group in PK population.

HI antibody will be summarized using geometric mean, minimum, median, and maximum of GMT values and Geometric Mean Fold Rise (GMFR; fold increase in GMT for Day 29 vs Baseline) by actual treatment group and each scheduled collection time. Also proportion of subjects with the titer values of Baseline <10 and Day 29 ≥ 40 , Baseline >40 , Day 29 >40 , GMFR ≥ 4 , and Baseline ≥ 10 and GMFR ≥ 4 will be summarized.

The values below the LLoQ (10) will be imputed as 5 and the imputed values will be used for summary table.

11.3.2 Genotype

Genotype results will be presented in data listing by treatment group and subtype (H1N1 HA, H1N1 NA, H3N2 HA, H3N2, NA) in ITTI population.

Screening (influenza A positive sample regardless of titer value) and the last influenza A positive sample in time with $> 4 \log_{10}$ vp/ml will be analysed.

11.3.3 Phenotype

Potential CT-P27 resistant variants will be selected by phenotypic virus titration assay. The result of this assay will be generated as a separate report.

Statistical Analysis Plan

Among potential variants, the samples for CT-P27 susceptibility and neuraminidase enzyme phenotyping assay will be selected in accordance with the central laboratory protocol. For potential variants, CT-P27 susceptibility assay and neuraminidase enzyme phenotyping assay will be performed to determine the half maximal effective concentration (EC₅₀) value for CT-P27 and the half maximal inhibitory concentration (IC₅₀) value for neuraminidase inhibitor (Oseltamivir), respectively. These values will be used to assess the resistance against CT-P27 and neuraminidase inhibitor. The fold resistance change which is the ratio of two resistance values will be presented with resistance values in data listing by treatment group in ITTI population. If one of values, EC₅₀ or IC₅₀, has the Upper Limit of Quantification (ULoQ) the value will be treated as limit of quantification for the calculation of fold resistance change. All of results in the listing will be presented with 3 decimal places.

12. Safety Analysis

All safety analyses will be performed in the safety population by actual treatment group presenting data on AEs, Clinical laboratory results (Hematology, Biochemistry, Urinalysis), Vital signs, Immediate Hypersensitivity, ECG, Physical examination, Weight, Pregnancy test, Chest X-ray, Suspicious ADE.

12.1 Adverse Events

An adverse event (AE) is any untoward medical occurrence in a subject enrolled (i.e., when the ICF is signed) into this study regardless to its causal relationship to study drug. An AE can, therefore, be any unfavorable and unintended sign (including an abnormal laboratory finding), symptom, or disease.

All AEs will be classified by SOC and PT according to the MedDRA version 20.1 or later and the version number will be shown as a footnote on the corresponding tables and listings. AEs will be graded for intensity according to the Common Terminology Criteria for Adverse Events (CTCAE) v 4.03 ([Appendix 14.2](#)).

Listings for AEs occurring during the study will be provided by actual treatment received. The listing will include the following information from the eCRF: SOC, PT and reported term; Start date/time; End date/time; Whether the event is classified as TEAE or TEAE due to Infusion Related/Anaphylactic Reaction (IRR) (Yes, No); Duration of AE in days (Duration= [End date-Start date] +1); Frequency (continuous, intermittent, transient, other with specified frequency); Outcome (recovered, recovered with sequelae, recovering, not recovered, fatal, unknown); Intensity (Grade 1(mild), Grade 2(moderate) Grade 3(severe), Grade 4(life-threatening), Grade 5(death)); Relationship to study drug (Definite, Possible, Probable, Unrelated, Not assessable); Action taken with study treatment (No action taken, Dose reduce, IP interrupted, IP withdrawn, Other with specified action); Other treatment (No treatment, Medication treatment, Non-medication treatment with specified treatment, Both medication and non-medication treatment with specified treatment); Whether a subject terminated from study due to this AE (Yes, No); Whether the event is serious (Yes, No); Whether the event is classified as secondary complication (Yes, No).

Events will be considered to be related if relationship is definite, possible, probable or not assessable for the study drug.

A summary table of overall AEs will be presented by actual treatment group, including the following:

- Total number of AEs, SAEs
- Number and percentage of subjects with at least one AE, SAE, TEAE, TESA, TEAE leading to study discontinuation, TEAE due to IRR, TEAE leading to death.

A SAE is defined as any AE occurring at any dose that results in any of the following outcomes; death, life-threatening, in subject hospitalization or prolongation of existing hospitalization, disability/incapacity, congenital anomaly in the offspring of a subject who received drug, other SAEs; important medical events that may not result in death, be life-threatening, or require hospitalization may be considered SAEs when, based upon appropriate medical judgment, they may jeopardize the subject or require medical or surgical intervention to prevent one of the outcomes listed in this definition.

Statistical Analysis Plan

All SAEs will be listed including the variables detailed in the listing for AEs above except whether the event is serious (Yes, No).

Furthermore, additional information of SAEs will be listed in a separate listing including following variables: SOC, PT and reported term; Start date/time; End date/time; Whether the event is classified as TEAE or TEAE due to IRR; Serious criteria (hospitalization initial, hospitalization prolonged, life-threatening, results in death, persistent or significant/incapacity, congenital anomaly or birth defect, other medically important serious event); Admission date/Discharge date for hospitalized subjects; Death date; Autopsy performance (Yes, No); Death certificate completion (Yes, No) for subjects resulted death; SAE abating after stopping the study drug (Yes, No, NA); SAE description; SAE reoccurring after reintroduction of the study drug (Yes, No, NA).

